11.3.1 Baseline Bellmunt Score

The Bellmunt prognostic risk factor score is a tool that is often used to predict treatment outcomes before initiating a secondline treatment regimen. Baseline Bellmunt Score will be computed as number or risk factor (0,1,2,or 3) out of the following:

- ECOG PS \geq 1
- Hemoglobin concentration < 10 g/dL
- Liver metastases present

11.4 Prior and Concomitant Medications

Medications administered to study participants during the on-study period are captured on a log CRF page. Medications are considered prior medications if they have a start date prior to the date of first dose of study medication or a partial start date which indicates the medication was begun prior to the first dose of study

treatment. Medications with missing start dates will be considered prior medications. If medication with missing start dates but the end date is after first dose of study treatment, it will be considered as concomitant medication as well. Concomitant medications are defined as medications administered to study participants on or after the first dose of study treatment and before the last dose of study treatment. A medication can be considered both prior and concomitant. Collected prior and concomitant medications will be coded using the World Health Organization (WHO) Drug Enhanced (version: 2018MAR01 DDE+HD B3 medical dictionary).

Prior and concomitant medications will be tabulated separately for the Safety population by Anatomical Therapeutic Chemical Classification and preferred drug name using counts and percentages. Summaries will be presented by cohort (including initial and contingent cohorts) and all cohorts combined. Prior and concomitant medications will be included in a patient data listing.

11.5 Medical History

Medical history will be tabulated by system organ class (SOC) and preferred term (PT) using counts and percentages for the Safety population. Medical history will be coded according to Medical Dictionary for Regulatory Activities (MedDRA, Version 21.0). Medical history will be listed by patient.

Baseline Signs and Symptoms

Signs and symptoms of the patient's cancer diagnosis and/or comorbidities present prior to Day 1 of study treatment dosing are recorded in the CRF as primary disease history.

11.6 Efficacy Analyses and Efficacy Variables

11.6.1 Objective Response Rate (ORR)

Disease assessments involving radiographic evaluations may be performed over the course of a few days. The date of response (Complete Response, CR; Partial Response, PR; Stable Disease, SD; or Not Evaluable, NE) will be recorded as the date of the last radiographic evaluation included in the series for that time point assessment. The date of progression (PD) will be recorded as the date of the first radiographic evaluation included in the series for that time point assessment to identify progression.

ORR will be categorized in accordance with RECIST v1.1. (Appendix 3) Objective Response Rate (ORR) is defined as the percent of patients documented to have a confirmed CR or PR as defined in Table 9.

Descriptive statistics (frequency and percentage) for ORR, CR, and PR will be presented. The 95% exact Clopper-Pearson CI of these response rates will be calculated. An exact test for single proportion (two-sided $\alpha = 5\%$) will be performed to test $H_0: ORR \leq 5\%$ against $H_1: ORR > 5\%$.

Best overall response (BOR) is defined as the best response among all overall responses (in the order CR, PR, SD, PD, and indeterminate NE) recorded from the start of study drug until disease progression/recurrence, or start of anti-cancer therapy, whichever comes first.

The status of best response of CR or PR must be confirmed by repeat tumor assessment within no less than 4 weeks according to RECIST version 1.1. If the status of CR or PR cannot be confirmed by repeat tumor assessment, the BOR of unconfirmed CR and PR will be determined per RECIST 1.1. The status of BOR of SD requires an on-study assessment after at least 42 days on treatment. Patients without a valid clinical response assessment will be assigned a best overall response of NE. No response will be counted after PD.

Table 9 lists out the different scenarios of confirmed response based on subsequent assessment. The status of SD requires an on-study assessment at least 42 days on study. Patients without a valid clinical response assessment will be assigned a best overall response of NE.

Table 9 Confirmed Response Based on Subsequent Assessments*

First Time Point Response**	Second Time Point Response	Confirmed Response (Best Response)*
PD	No further evaluation	PD
NE	PD	PD
CR	PD	SD or PD (1)
PR	PD	SD or PD (1)
SD	PD	SD or PD (1)
CR	CR	CR
CR	NE **	SD or NE (2)
PR	CR	PR
PR	PR	PR
PR	SD (3)**	SD
PR	NE **	SD or NE (2)
SD	CR	SD
SD	PR	SD
SD	SD	SD
SD	NE	SD or NE (2)
First Time Point Response**	Second Time Point Response	Confirmed Response (Best Response)*
NE	CR	SD
NE	PR	SD
NE	SD	SD
NE	NE	NE

* A Best Response of SD can only be made after the patient is on-study for a minimum of six (6) weeks (42 days). If the patient is on-study less than six (6) weeks (42 days), any tumor assessment indicating stable disease before this time period will have a Best Response of NE unless PD is identified.

** Subsequent documentation of CR may provide confirmation of a previously identified CR for patients where the second integrated response was NE. Subsequent documentation of PR may provide confirmation of a previously identified PR for patients where the second integrated response was NE or SD. If the third Time Point Response (TPR) confirms the CR (or PR) then the Confirmed Response will be CR (or PR). For this study, only one (1) intervening NE is allowed between CRs/PRs. For example: CR NE CR = CR; PR NE PR = PR. Additionally, one (1) SD is allowed between PRs (e.g., PR SD PR = PR).

(1) Best response will be SD if the first TPR is after at least six (6) weeks (42 days) on-treatment. Otherwise, the best response will be PD.

- (2) Best response will be SD if the first TPR is after six (6) weeks (42 days) on-study. Otherwise, the best response will be NE.
- (3) TPR is SD if the increase from the first to the second assessment does not qualify for PD.

For patients with unconfirmed CR/PR and who subsequently drop off the study, the best overall response will be SD.

Descriptive statistics (frequency, percentage) for best overall response (CR, PR, SD, PD, NE) based on response assessments by the investigator will be presented.

The primary analysis will be conducted in the Full Analysis Population and supportive analysis will be presented in the Clinical Activity Evaluable population.

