9.3 Analysis Populations

9.3.1 Full Analysis Population

The full analysis population (FAP) is defined as all patients who receive one dose of all study treatments (i.e. at least one dose of both sitravatinib and nivolumab for Cohorts 1 through 8, or at least one dose each of sitravatinib, pembrolizumab and enfortumab for Cohorts 9 and 10).

The primary efficacy analyses of the primary and secondary efficacy endpoints will be performed in the FAP for all cohorts. In addition, the FAP population will be used 1) in making decisions to expand the study to the third stage of enrollment for Cohorts 1 through 4, and 2) for the interim futility analysis for Cohorts 7 and 8.

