9.4 Efficacy Endpoint Definitions and Analyses

9.4.1 Objective Response Rate

Objective disease response will be categorized in accordance with RECIST v1.1 ([Appendix 4](#)). Objective Response Rate (ORR) is defined as the percent of patients documented to have a confirmed Complete Response (CR) or Partial Response (PR).

Descriptive statistics (frequency and percentage) for ORR, CR, and PR will be presented. The exact 95% CI of these response rates will be calculated. An exact test for single proportion (two-sided $\alpha = 5\%$) will be performed to test $H_0: ORR \leq 5\%$ against $H_1: ORR > 5\%$. Other details will be described in the SAP.

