7.1.5 Hypothesis and Sample Size Considerations

This Phase 2 study will use Predictive Probability Designs (Lee-2008) for initial cohort 1 and 2. In summary, Cohorts 3 and 4 will also use Predictive Probability Designs with the same assumptions as the initial cohorts (Section 6.1), Cohorts 5 and 6 will use Predictive Probability Designs with revised assumptions, Cohorts 7 and 8 will use confidence interval method with the revised assumptions, the lead-in dose escalation portion of Cohort 9 will use the mTPI-2 design (Guo-2017; Appendix 2).

In creating the statistical designs, the Type 1 error (α) is constrained to <0.05 and Power ($1-\beta$) is constrained to ≥ 0.90 .

7.1.5.1 Cohort 1 and 2:

ORR in accordance with RECIST v1.1 is the primary endpoint. The ORR using nivolumab in the population of advanced/metastatic urothelial carcinoma who experienced disease progression on or after treatment with a checkpoint inhibitor is assumed to be 5% (p_0); thus, this rate is considered uninteresting. The target ORR using sitravatinib in combination with nivolumab in this study population is 30% (p_1). Stage 1 of enrollment will include a minimum of 9 evaluable patients in each cohort. Patients included in the evaluable population will have at least one on-study disease assessment prior to discontinuation; patients who discontinue treatment due to adverse events or withdrawal of consent prior to the first on-study disease assessment will not be included in the evaluable population. With exactly 9 evaluable patients at Stage 1, if at least 1 patient has an Objective Response, 8 additional evaluable patients will be enrolled in the treatment cohort, for a total sample size of 17 evaluable patients. If at least 3 Objective Responses are observed in a treatment cohort, further investigation may be warranted. If the true ORR is 5% (null hypothesis), the probability of early termination during the study is 0.63; the Type 1 error is equal to 0.0466 and the power is equal to 0.9045.

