In the event that results in the initial study cohorts are of high interest for efficacy, one or more cohorts in patients who have not previously received checkpoint inhibitor therapy (CIT-naïve) may be added to the study. Decisions for implementation of additional cohorts in the study will be made in collaboration with the Investigators and documented for Regulators and Institutional Review Boards by an Administrative Letter to Investigators.

Based on the evolving treatment landscape of urothelial carcinoma and early efficacy and safety results from active study cohorts, and in consult with Investigators, both Cohort 5 and Cohort 6 described in this section were implemented by an Administrative Letter dated May 2019.

The ORR using nivolumab in the population of advanced/metastatic urothelial carcinoma who have not previously received treatment with a checkpoint inhibitor therapy is assumed to be 20% (p_0); thus, this rate is considered uninteresting. The target ORR using sitravatinib in combination with nivolumab in this study population is 40% (p_1). Stage 1 of enrollment will include approximately 24 evaluable patients in each cohort. Patients included in the evaluable population will have received treatment with both sitravatinib and nivolumab and will have at least one on-study disease assessment prior to discontinuation; patients who discontinue treatment due to adverse events or withdrawal of consent prior to the first on-study disease assessment will not be included in the evaluable population. With exactly 24 evaluable patients at Stage 1, if at least 6 patients have Objective Responses, enrollment of 21 additional evaluable patients is needed in the treatment cohort, for a total sample size of 45 evaluable patients. If at least 14 Objective Responses are observed in a treatment cohort, further investigation may be warranted. If the true ORR is 20% (null hypothesis), the probability of early termination during the study is 0.66; the Type 1 error is equal to 0.0483 and the power is equal to 0.9001.

The exact stopping rules for futility for both cohorts will be calculated based on the Predictive Probability Design, once the exact number of patients evaluable at Stage 1 is known. The aim is to include approximately 24 evaluable patients at Stage 1. The Sponsor retains the option to take more than one look at the data when making decisions based on the PPD method to expand cohorts.

7.1.5.4 Cohort 7 and 8:

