In the event that results in the initial study cohorts are of high interest for efficacy, one or more cohorts in patients with documented disease progression on or after a PD-(L)1 checkpoint inhibitor therapy and an antibody-drug conjugate (ADC; e.g. enfortumab vedotin, sacituzumab govitecan), in any order or in combination together. Decisions for implementation of additional cohorts in the study will be made in collaboration with the Investigators and documented for Regulators and Institutional Review Boards by an Administrative Letter to Investigators.

Based on the evolving treatment landscape of urothelial carcinoma in particular with the clinical activity of ADCs, and early efficacy and safety results from active study cohorts, and in consult with Investigators, both Cohort 7 and Cohort 8 described in this section were implemented by an Administrative Letter dated September 2019.

The ORR using taxanes in the population of advanced/metastatic urothelial carcinoma who have previously received treatment with a checkpoint inhibitor therapy and ADC is assumed to be 10%; thus, this rate is considered uninteresting. The design for Cohort 7 and Cohort 8 will utilize a 95% confidence interval to exclude an ORR of 10%. Assuming sitravatinib in combination with nivolumab treatment will result in an ORR of at least 25% in this treatment setting, a sample size of approximately 55 evaluable patients would be sufficient for the lower bound of a 2-sided 95% confidence interval (Clopper-Pearson method) to exclude an ORR of 10%.

The design will include a non-binding stopping rule for futility derived using East[®] software v6.5 to control the Type 2 error rate of 0.117. The Type 2 error spending function is based on the Rho family with parameter 2.0. The futility analysis will be conducted when approximately 17 evaluable patients (approximately 30% of the total number of patients) are available for the response assessment. The futility bound will be 1 or fewer observed responses among the first 17 patients.

7.1.5.5 Cohort 9:

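### The only ORR test in the SAP uses a 5% null for every cohort, but the design null is 20% in Cohorts 5-6 and 10% in Cohorts 7-8

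*SAP*

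**What the plan says.** SAP 11.6.1 plans response frequencies, exact Clopper-Pearson 95% intervals and one test: "An exact test for single proportion (two-sided $\alpha = 5\%$) will be performed to test $H_0: ORR \leq 5\%$ against $H_1: ORR > 5" per cent. Protocol 9.4.1 has the same sentence: an exact test "will be performed to test $H_0: ORR \leq 5\%$ against $H_1: ORR > 5" per cent. Neither section names a cohort or refers to cohort-specific nulls. SAP 11.0 presents tables for each cohort, contingent cohorts included, and for all cohorts combined. Protocol 9.3.1 adds: "The primary efficacy analyses of the primary and secondary efficacy endpoints will be performed in the FAP for all cohorts".

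The design sections set different nulls:

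- **Cohorts 1-4** (SAP 7.1.5.1-7.1.5.2): null 5%, target 30%. Continue with at least 1/9; go with at least 3/17; "the Type 1 error is equal to 0.0466 and the power is equal to 0.9045".
- **Cohorts 5-6** (SAP 7.1.5.3): the nivolumab ORR "is assumed to be 20% (p_0); thus, this rate is considered uninteresting", target 40%. The Stage 1 rule begins "With exactly 24 evaluable patients at Stage 1, if at least 6 patients have Objective Responses", and 21 more patients are then enrolled. Go with at least 14/45; "the Type 1 error is equal to 0.0483 and the power is equal to 0.9001".
- **Cohorts 7-8** (SAP 7.1.5.4): "The design for Cohort 7 and Cohort 8 will utilize a 95% confidence interval to exclude an ORR of 10" per cent, with about 55 patients, an assumed ORR of 25%, and a non-binding futility bound of 1 or fewer responses in the first 17.

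**The concern.** A test against 5% asks the design question only in Cohorts 1-4. In Cohorts 5-8, rejection shows that ORR exceeds 5%, which says nothing about exceeding the 20% or 10% that the plan calls uninteresting. Followed literally, 11.6.1 would put a significant p-value on the primary endpoint beside a result that fails the cohort's own design criterion. That includes a Cohort 5 or 6 stopped for futility at 5/24, because nothing limits the test to cohorts that continue.

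**Working it through.** All figures are exact binomial. T(n, r, p) is P(X ≥ r) for X ~ Bin(n, p). For a two-stage rule (n1, continue with at least c; total n, at least r):

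P = Σ over x ≥ c of P(X1 = x) · P(X2 ≥ r − x), with X1 ~ Bin(n1, p) and X2 ~ Bin(n − n1, p).

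**1. Reproduce the plan.**

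| Cohorts | Rule | Type 1 error | Power |
|---|---|---|---|
| 1-4 | ≥1/9, ≥3/17; 5% vs 30% | 0.0466 | 0.9045 |
| 5-6 | ≥6/24, ≥14/45; 20% vs 40% | 0.0483 | 0.9001 |

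Both rows agree with the SAP. The Cohort 5-6 early termination probability is P(X ≤ 5 | 24, 0.20) = 0.656, stated as 0.66. For Cohorts 7-8 the smallest count whose interval excludes 10% is 11/55 (lower limit 10.4%; 10/55 gives 9.1%).

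**2. Thresholds of the written test (null 5%).** The SAP does not define the exact two-sided p-value, so three versions were tried: doubled tail, minimum likelihood, and one-sided 5%.

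| Result | Upper tail | Doubled | 95% CI lower limit | Rejects 5%? |
|---|---|---|---|---|
| 5/45 | 0.0729 | 0.146 | 3.7% | no |
| 6/45 | 0.0239 | 0.0477 | 5.05% | yes |
| 6/55 | 0.0560 | 0.112 | 4.1% | no |
| 7/55 | 0.0193 | 0.0386 | 5.27% | yes |
| 5/24 | 0.0060 | 0.0119 | 7.1% | yes |

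These answers are the same under all three versions. At n = 24 the other two versions also reject at 4/24 (upper tail 0.0298).

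**3. Probability of rejecting when the true ORR equals the design null.**

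- *Cohorts 5-6, true 20%.* Passing Stage 1 takes at least 6 responses and 6/45 already rejects, so every cohort that reaches 45 rejects: P(X ≥ 6 | 24, 0.20) = 0.344. The 14/45 rule gives 0.0483. If stopped cohorts are also tested, P(X = 5 | 24, 0.20) = 0.196 is added: 0.344 + 0.196 = 0.540 (doubled tail). Under the versions that reject at 4/24, P(X = 4 | 24, 0.20) = 0.196 is added again: 0.736.
- *Cohorts 7-8, true 10%.* T(55, 7, 0.10) = 0.310, or 0.241 if the futility stop is followed. The rule of excluding 10% gives T(55, 11, 0.10) = 0.019 (0.018 with the stop).

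**4. Sensitivity to the denominator.** The counts 24, 45 and 55 are evaluable patients, whereas the primary analysis uses the Full Analysis Population.

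- Cohorts 5-6, assuming 1 to 12 added non-responders (46-57): the threshold is 6 or 7, and the probability is 0.343-0.344.
- Five responses still reject at any size from 24 to 33 (doubled p 0.0461 at 33, 0.0518 at 34).
- Cohorts 7-8, assuming 55-65 patients all at a true 10%, no stop: 0.22-0.34 by the doubled tail. Minimum likelihood keeps the threshold at 7 up to 65, where the probability is 0.48.

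**5. The same test with the design null (doubled tail).**

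| Cohorts | Null | Threshold | Upper tail | Power |
|---|---|---|---|---|
| 5-6 | 20% | 15/45 | 0.02499 | 0.847 at 40%, two-stage |
| 7-8 | 10% | 11/55 | 0.0189 | 0.845 at 25% (0.821 with stop) |
| 1-4, ending at 17 | 5% | 4/17 | 0.0088 | 0.790 at 30%, two-stage |

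Against 20%, 14/45 has upper tail 0.0521 and does not reject. Against 20%, 5/24 has upper tail 0.540.

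**The case against.** Four arguments can be made for the plan.

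1. *The sentence was meant for Cohorts 1 and 2.* Protocol 9.1 introduces its hypothesis for those cohorts and sends the others to the appendices. Appendices 6 and 8 announce changes to hypothesis and sample size. That is probably how the sentence arose, but those changes appear under sample size and do not touch the test in 9.4.1. SAP 11.6.1, which postdates the contingent cohorts, repeats the test without a label.
2. *No decision depends on it.* Enrollment follows the go rules, and for Cohorts 7-8 the interval against 10% is both prespecified and reported. This stands: a careful reader can make the right comparison, and no document makes the p-value a success criterion. It limits the consequence to the reported inference. For Cohorts 5-6 the SAP states no interval criterion.
3. *The probabilities are conditional.* They take exactly 24 patients and a single look at Stage 1. The SAP says approximately 24, recalculates the rule for the actual number, and lets the sponsor look more than once. The 0.540 is also specific to the doubled tail. These labels are needed, but the alternative p-value definitions give a larger figure (0.736).
4. *The repair creates a mismatch.* With 15/45 required, a cohort meeting the 14/45 go rule can miss significance. True, but Cohorts 1-4 already have this gap (3/17 to go, 4/17 to reject). Restricting the 5% test to Cohorts 1-4 would be a smaller edit, but it would leave Cohorts 5-8 without a test.

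**Conclusion.** The concern holds. As written, the only test of the primary endpoint uses a null below the design null in four of the eight sitravatinib-nivolumab cohorts. At the design null it rejects with probability 0.344 in Cohorts 5-6, about seven times the 0.0483 of the go rule (0.344/0.0483 = 7.1). In Cohorts 7-8 the probability is 0.31, or 0.24 with the futility stop, against 0.019. For Cohorts 5-6 the test adds nothing once Stage 1 is passed.

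The 0.344 assumes one look at exactly 24 patients, with confirmed responses counted at Stage 1. Protocol section 3 lets unconfirmed responses start an expansion; continuing to 45 on those can only raise it. The 0.540 further assumes that stopped cohorts are tested with a doubled-tail p-value. Reading the sentence as applying to every cohort rests on the absence of any restriction. Because the interval is reported too and enrollment does not use the test, this should be corrected but does not undermine the design.

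**What to change.** In SAP 11.6.1 and Protocol 9.4.1:

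- Replace the single null with 5% for Cohorts 1-4, 20% for Cohorts 5-6 and 10% for Cohorts 7-8. Keep the two-sided exact test and the Clopper-Pearson interval in the Full Analysis Population.
- Define the two-sided p-value as twice the smaller tail, so that it always agrees with the interval.
- State that no ORR test applies to the Cohort 9 lead-in or to all cohorts combined (interval only). Any Cohort 9 expansion or Cohort 10 analysis would use the 45% null of Protocol Appendix 9, although SAP Figure 1 says these will not open.
- Give the thresholds and power of step 5. Say that the stated powers 0.9045 and 0.9001 describe the go rules in evaluable patients, not this test.

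The cost is wording and a few lines of code, with no extra patients. Protocol section 9 requires an amendment for a major change to the primary analysis. The drawback is stringency: treated patients without a scan raise the bar. If five are added to the 45 as non-responders (an assumption), Cohorts 5-6 need 17/50, and power is 0.67 at an ORR of 40% among evaluable patients.

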11.6.2 Duration of Response (DOR)

Duration of response (DOR) in months is defined as the time from date of the first documentation of confirmed objective response (CR or PR) to the first documentation of objective PD or to death due to any cause in the absence of documented PD (i.e., $\min[\text{PD date, death date}] - \text{date of the first observation of response} + 1$)/30.4375. Duration of response will only be calculated for the subgroup of patients achieving a confirmed CR or PR.

DOR will be summarized descriptively using the Kaplan-Meier estimate. The median, 25th percentile, and 75th percentile of DOR and their two-sided 95% CI (Brookmeyer & Crowley, 1982) will be calculated where appropriate. In addition, minimum and maximum will also be displayed. Kaplan-Meier plots will be provided for DOR.

DOR will be based on response assessments by Investigator. DOR will be conducted in the CAE population who have confirmed CR or PR.

